The BRIDGE study - Bronchiectasis Research Involving Databases, Genomics and Endotyping to match the right treatment to the right patient.

Signatures

The undersigned confirm that the following protocol has been agreed and approved by the Sponsor and that the Chief Investigator agrees to conduct the study in compliance with this approved protocol and will adhere to the principles of GCP, the Sponsor SOPs, and any other applicable regulatory requirements as may be amended from time to time.

[name] [name]

D

02.04.25

Chief Investigator

Signature

Date

1.0 Summary of Study:

Study Title	The BRIDGE study - Bronchiectasis Research Involving	
	Databases, Genomics and Endotyping to match the right	
	treatment to the right patient.	
Study Design	Prospective observational cohort study	
Study Population	Adults with bronchiectasis	
Sample Size	2500 internationally (600 UK)	
Planned study period	8 years	
Clinical phase duration	5 years	
Primary	Objectives	
C	To determine molecular endotypes of bronchiecta guide response to treatment.	asis which can
Secondary	Objectives	Outcome
	 To determine molecular endotypes of stable bronchiectasis To determine the causes and inflammatory profiles of bronchiectasis exacerbations To validate candidate biomarkers of stable and exacerbation endotypes to use in stratified medicine To perform in-vivo or in-vitro proof of concept studies using phenotypic data to identify patient populations likely to benefit in future randomized controlled trials 	Measures Detailed endotypes in bronchiectasis which can guide response to treatment.

1.1 Background: Bronchiectasis is a common disabling and heterogeneous disease that has been neglected in terms of basic and clinical research. Recent controlled

trials have failed to achieve their primary end-points, likely because the optimal patient population to benefit from antibiotic, mucoactive and anti-inflammatory drugs has not been identified. This study aims to explore the clinical, microbiological, inflammatory and functional heterogeneity of the disease with the aim of identifying patient endotypes for stratified medicine.

1.2 Study aims and objectives

- 1. To determine the molecular endotypes of bronchiectasis during stable disease
- 2. To determine the causes and inflammatory profiles of bronchiectasis exacerbations
- 3. To validate candidate biomarkers of stable and exacerbation endotypes to use in stratified medicine
- 4. To perform in-vivo and in-vitro proof of concept studies using phenotypic data to identify patient populations likely to benefit in future randomized controlled trials

1.3 Study Design: Observational Cohort study

1.4 Study methods:

Patients with bronchiectasis will be recruited into an observational study, the objectives of which will be to:

Aim 1 will define and validate endotypes of stable bronchiectasis by studying approximately 2500 patients with bronchiectasis. Clinical data (described in the data collection section), sputum microbiome, sputum proteomics, and systemic and sputum inflammatory marker measurement will be incorporated for analysis. A substudy (n=400) will be performed using primary airway epithelial cells. Patients will have brushings of the inferior nasal turbinate with assessment of % ciliation, ciliary beat frequency and pattern by high speed video microscopy before and after culture.

Aim 2 will replicate the phenotyping approach to stable patients with 60 patients during exacerbation. This will identify changes from baseline in microbiota, proteomic and other markers associated with onset of exacerbation and allow classification of clusters of exacerbation.

Aim 3 we will externally validate candidate phenotype/endotypes in registered ethically approved external biobanks and aim to demonstrate that validated markers be linked to potential treatment responses for use in stratified medicine trials.

In total we will recruit approximately 2500 patients for study. These patients will attend one of the participating study centres at least once and undergo sampling along with collecting of clinical data. Patients will be asked to consent for their samples to be linked to data held on an existing pan European bronchiectasis database (the EMBARC registry).

1.5 Nature of outputs and outcomes/results expected:

This study will aim to establish detailed endotypes in bronchiectasis which can guide response to treatment.

2.0 Study background:

Bronchiectasis has been described as one of the most neglected diseases in respiratory medicine. (1,2) There are no licensed treatments, and the burden of disease is high and increasing. In the UK, bronchiectasis affects 485 per 100,000 men and 566 per 100,000 women and the prevalence has increased by approximately 40% in the past decade.(3) Traditional bronchiectasis guideline approaches to treatment are focussed on airway infection (long term oral/inhaled antibiotic treatments), mucus clearance (physiotherapy, devices, mucoactive drugs) and airway inflammation (inhaled corticosteroids, macrolides).(1) Clinical trials have failed to demonstrate clear benefit of inhaled antibiotics across multiple compounds.(4-6) Macrolides reduced the frequency of exacerbations in 3 randomised trials, but up to 40% of patients do not respond to treatment in practice.(7-10) Mucoactive drugs are not widely used and clinical trials of mannitol have failed to meet their primary end-points, DNAse was found to be harmful in bronchiectasis despite benefits in cystic fibrosis, while hypertonic saline has not shown clear benefits over 0.9% saline.(11-14) A Cochrane review concluded that there is insufficient evidence to support the use of inhaled corticosteroids.(15) The failure of therapies to translate from cystic fibrosis to bronchiectasis is thought to be due to the greater inflammatory, microbiological, radiological and aetiological heterogeneity in bronchiectasis. (16)

Achieving success in developing new therapies for this disease requires detailed translational research to define patient phenotypes and endotypes. Personalised, stratified or precision medicine is increasing advocated across a range of conditions to improve targeting of therapies. (17-20).

This study aims to phenotype and endotype bronchiectasis during stable disease and exacerbations, to develop strategies for personalised medicine.

3.0 Study Objectives:

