14.0 Statistics and data analysis

14.1 Sample size calculation

The sample sizes for each element have had to be chosen subjectively, balancing potential detail against practical limits. As all the sample sizes are greater than 100, they should contain individuals from all subgroups containing more than 10% the population. Study aims one and two classify individuals into groups on the basis of their characteristics, so any realistic power calculations would involve strong assumptions about the distributions and correlations of the measured variables and therefore require data that will be collected during the study. Until that has been collected, the calculations would effectively be guesswork. The investigations for aim three will use as many relevant individuals as are available in the databases and, along with those for aim 4, will be highly dependent on the findings in the earlier stages.

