14.2 Proposed analyses

For study aim one, to identify endotypes of bronchiectasis, an unbiased cluster analysis approach will be taken. As the number of practically distinguishable endotypes is unknown, the stability of representations containing different numbers of clusters will be compared, and the importance of the various characteristics to their separation will be investigated.

Study aim 2 will take a similar approach to samples from a smaller number of the patients during exacerbation. As these individuals are a subset of those examined for aim 1, their stable disease endotypes will be considered for inclusion in the cluster analysis. Descriptive statistics will be used to describe the qualities of typical members of each cluster and the differences between clusters.

For aim 3, the patterns identified in the first two parts of the study will be used to classify data from external biobanks and generalized linear models will be used to look for differences in those individuals' responses to treatment and disease trajectories. The classifications will also be applied to the identification of potential participants and samples for the proof of concept studies under aim 4. The analysis of those studies will depend on their particular forms and outcomes but follow generally recognized best practice.

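### Aim 1 promises to validate the stable endotypes, but no analysis stated in the protocol tests whether the clusters recur in patients who did not form them

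*Protocol*

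**What the plan says.** Section 1.4 sets the task: "Aim 1 will define and validate endotypes of stable bronchiectasis by studying approximately 2500 patients with bronchiectasis". The list of aims in section 1.2 is narrower: "To determine the molecular endotypes of bronchiectasis during stable disease". Secondary objective 1 in section 3.2 also speaks only of determining the endotypes.

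Section 14.2 gives the analysis: "For study aim one, to identify endotypes of bronchiectasis, an unbiased cluster analysis approach will be taken". Two supporting steps follow. The first deals with how many clusters to keep, which is not known in advance: "the stability of representations containing different numbers of clusters will be compared". The second asks what drives the clusters apart: "the importance of the various characteristics to their separation will be investigated". For Aim 1 it names no group of patients, sites or countries to be kept apart and no criterion for replication.

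Validation in other patients appears under a different aim. Section 1.4 says: "Aim 3 we will externally validate candidate phenotype/endotypes in registered ethically approved external biobanks". Section 14.2 describes how: "the patterns identified in the first two parts of the study will be used to classify data from external biobanks", after which generalized linear models compare response to treatment and disease course.

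Section 9.2 adds that not every laboratory procedure will be run on every sample, and that procedures done at site depend on what each site can do.

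**The concern.** Clusters are built to be far apart in the data that produced them. Finding that many characteristics differ between them, in the same patients, follows from the method and is not evidence that they exist. Stability under a change in the number of clusters is more informative, but it still uses the same patients and, in 14.2, serves to choose that number. If assays or sampling differ between sites, a stable solution may partly be a map of sites.

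The primary objective (section 3.1) is the endotypes themselves, and the later aims use them. Under 14.2, Aim 2 may enter the stable endotypes into its own clustering, Aim 3 classifies external patients with the patterns found, and Aim 4 uses the classifications to pick participants and samples. A solution reported as validated after Aim 1 would carry more authority into those steps than the stated analysis can give it.

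**Working it through.** **1. The plan's own figure.** There is no calculation behind 2500 to reproduce. Section 14.1 says: "The sample sizes for each element have had to be chosen subjectively". Its one numerical statement is that samples above 100 should include members of every subgroup above 10%. This is sound: 1 − 0.9^100 = 0.99997. It concerns whether a subgroup is present, not whether a cluster is validated.

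**2. The passages side by side.**

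| Place | Task or analysis | Patients |
|---|---|---|
| 1.2, 3.2 | determine endotypes | not stated |
| 1.4, Aim 1 | define and validate | about 2500 |
| 14.2, Aim 1 | cluster, compare stability, examine separation | no separate group named |
| 1.4, Aim 3 | validate candidates externally | external biobanks |
| 14.2, Aim 3 | assign to existing classes, model outcomes | external biobanks |

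The last row uses new patients but a fixed rule. Everyone receives a class whether or not the classes exist there. A difference in outcome between classes could also come from a continuous severity gradient cut into pieces. Recurrence needs the new patients to be clustered afresh and compared with the projected labels, and no row does that.

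**3. What same-patient checks show when there are no groups.** Assumptions are mine: n = 2500, 20 Gaussian variables sharing three common factors, no true clusters, k-means, one simulated data set. Agreement is the mean adjusted Rand index over 10 bootstrap samples or 10 random 1250/1250 splits. Separation is by F-test at 0.05/20.

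| Clusters | Variables separated | Bootstrap stability | Split-sample agreement |
|---|---|---|---|
| 2 | 19 of 20 | 0.89 | 0.82 |
| 3 | 20 of 20 | 0.62 | 0.37 |
| 4 | 19 of 20 | 0.86 | 0.68 |
| 5 | 19 of 20 | 0.59 | 0.51 |

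Separation is nearly complete throughout, and stability looks good at two and four clusters.

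**4. How far this depends on the markers.** Further runs without true groups, n = 2500:

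- Uncorrelated markers (20 or 200 markers, 2 to 4 clusters, 1900 to derive and 600 held out): stability 0.02 to 0.17, held-out agreement 0.00 to 0.12. Both checks expose the failure.
- One common factor: held-out agreement 0.59 to 0.94 in one set of runs and 0.36 to 0.87 in another. Neither range would reliably expose it.
- Two to five factors: held-out agreement 0.04 to 0.79.
- Country-level shifts added: same-patient stability usually 0.88 to 1.00 (0.47 to 0.58 in two settings), leave-one-country-out agreement 0.00 to 0.45. Here only the left-out check exposes it. The protocol gives no figures for such shifts, so their size is assumed.

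**5. Whether a left-out check is feasible.** Sections 1.0 and 8.0 give 600 UK patients of 2500, so 2500 − 600 = 1900 elsewhere. An endotype of 10% would have about 0.10 × 600 = 60 UK and 0.10 × 1900 = 190 non-UK members. Section 8.0 calls the recruitment numbers indicative.

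**The case against.** Four points weigh on the other side.

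**Aim 1 is not clustering alone.** A reader might infer that separation is the only check. It is not: the stability comparison is a recognised form of internal cluster validation, and with uncorrelated markers it would expose a false solution. What remains is that it uses the same patients and can look good under correlation or site differences.

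**External validation is planned.** A reader might infer that the study never takes its endotypes to other patients. The documents do not support that: Aim 3 does so, and its wording in 1.4 still calls them candidates. What remains is that the Aim 3 analysis in 14.2 tests association with outcomes rather than recurrence, and that Aim 1 claims validation in its own right.

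**A hold-out may be in a statistical analysis plan.** Only the protocol was available, and its silence does not show that no split exists. The point does not rest on a missing detail. It rests on 1.4 promising something that 1.2, 3.2 and the Aim 1 analysis in 14.2 do not.

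**A left-out check is no proof.** It is tempting to say that testing on unseen patients would unmask false endotypes. The runs with a common factor contradict this. Conversely, low agreement between countries may reflect different assays or sampling (9.2) rather than false endotypes, and small countries cannot be clustered reliably. All of this stands, and it limits how the result may be read.

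**Conclusion.** The concern holds in a limited form. Section 1.4 claims that Aim 1 validates the stable endotypes; sections 1.2 and 3.2 do not; and no analysis stated in 14.2, under Aim 1 or Aim 3, tests whether the clusters recur in patients who did not shape them.

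The size cannot be read from the protocol, which gives no marker correlations or site differences. Under the assumptions above, same-patient stability reached 0.89 with no groups at all, and usually 0.88 to 1.00 with country shifts, where left-out agreement was at most 0.45. The simulations are illustrative, use k-means only, and show what can happen rather than what will. With uncorrelated markers and no site effects, the planned stability comparison would be enough to raise the alarm. It is a correction worth making before the endotypes are reported, not a flaw that undermines the cohort.

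**What to change.** Preferred: add internal-external validation to 14.2.

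1. Leave out one country or group of sites large enough to cluster, for example UK against non-UK.
2. Derive and freeze the classification on the rest.
3. Project it onto the left-out group, and cluster that group afresh.
4. Report agreement for each endotype, then rotate.
5. Take the final endotypes from all 2500.

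State that recurrence is necessary but not sufficient, because correlated markers can give moderate to high agreement without true groups. Read disagreement alongside known differences in site procedures.

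The cost is analysis time, some text in 1.4 and 14.2, and imprecise agreement in small groups. Rotation gives up no patients. A single permanent split of 1900 and 600 would instead widen discovery standard errors by √(2500/1900) = 1.147, about 15%.

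If this is not done, delete the validation claim from Aim 1 in 1.4, so that it matches 1.2 and 3.2, and call the endotypes candidates until Aim 3. That changes no number.

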3.1 Primary Objective

To determine molecular endotypes of bronchiectasis which can guide response to treatment.

3.2 Secondary Objectives

- 1. To determine molecular endotypes of stable bronchiectasis
- 2. To determine the causes and inflammatory profiles of bronchiectasis exacerbations
- 3. To validate candidate biomarkers of stable and exacerbation endotypes to use in stratified medicine
- 4. To perform in-vivo or in-vitro proof of concept studies using phenotypic data to identify patient populations likely to benefit in future randomized controlled trials

4.0 Study start date: August 2018

5.0 Study duration: 8 years

6.0 Study outline

Type of visit	Screening and study V1 (n=2500)	Study visit procedures +/- 3 month V2-V4 (N=2500)	Exacerbation Visit (=<72 hours of commencing exacerbation medication)* * (Approx. N=300)
	Single visit	Vicit Months	
Timeline	Month 0	12, 24 & 36	
Informed Consent	х		
Inclusion/Exclusion Criteria Check	х		
Medical History	Х	X	
Record Concomitant Medications	x	x	x
Height	Х		
Weight	Х		
FENO (only at selected sites with appropriate equipment available to do this)	х	x	
Post-bronchodilator spirometry	x	x	x
Bronchiectasis quality of life questionnaires (QOL-B, BIM (UK & Spain only), BHQ and CAAT	x	х	X BIM only

Patient Global			
Impression Scale –	Х	х	
Severity (PGI-S)			
Patient Global			
Impression Scale –		х	
Change (PGI-C)			
Stool samples for	V	Y	v
storage	X	x	^
Research Blood	v		
Samples	^	^	^
Nasopharyngeal	v	v	
Swabs for storage	^	^	Х
Buccal swab if	v		
needed	^		
Spontaneous			
sputum samples or	Х	Х	Х
induced if required			
Saliva samples	v		Y
(optional)	^		X
Adverse Event	Х	Х	Х
reporting			
Clinical			
Bronchoscopy			
samples (optional			
blood, sputum,			
biopsies, brushings			
bronchial alveolar			
lavage (BAL)			
fluid***			
Cilia sub-study	V1	V2-V4	Exacerbation
Sind Sub Study			
Nasal brushings	Х	Х	Х

*Screening and visit 1 will be combined into a single visit. Exacerbation visits are optional as participants treated by their GP or taking a home supply of antibiotics may choose not to attend for an exacerbation visit.

** It will not be considered a breach if the visit window for any type of study visit must be rearranged for patient/team convenience or clinical significance, for e.g. if an exacerbation visit

is still deemed relevant to complete by CI/PI after 72 hours because patient is not responding to treatment then that exacerbation visit could still be carried out. *** As and when available

7.0 Study flow chart:

8.0 Study Design:

This is a multi-centre study performed through the EMBARC consortium. Data and samples will be collected from sites around the world. Ethical approval of this protocol will be sought at country level.

The UK sites will aim to recruit 600 patients over the course of the study with 2500 recruited world-wide. These numbers are indicative and we reserve the right to recruit more or less patients in the UK and elsewhere according to study need.

Patients will be recruited whilst clinically stable and asked to attend an annual visit at a clinical research facility for the research procedures outlined below. In addition, during an exacerbation individuals will be invited to attend the clinical research facility or to donate surplus samples through their local hospital or GP.

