Cilia sub study: At sites in the UK and other sites internationally (where the techniques are available) individuals will be invited to take part in the cilia sub-study. This invitation will be made at the same time as invitation to the main study and will involve additional sampling. Nasal brushing(s) will be taken. This involves removing surface cells from the mucosal lining of the nose with a small cytology brush. Eligible individuals will be invited to take part in the cilia sub study at visit 1 of the main study.

Exacerbation study: Patients will be included in the exacerbation part of the study if they present with an exacerbation during the 3 year study duration which meets the following criteria: At least three of the following: 1) Increased cough 2) Increased

sputum volume or change in sputum consistency 3) Increased sputum purulence 4) Increased breathlessness and/or decrease exercise tolerance 5) Fatigue and/or malaise 6) Haemoptysis, with symptoms lasting for at least 48 hours and requiring treatment with antibiotics. (note that patients may be seen in the first 24 hours of symptoms if appropriate as long as the physician believes that the patient has an exacerbation and that symptoms will last for at least 48 hours).

At this time the individual will have the option to attend the study centre to provide samples or if this is not possible surplus clinical sputum and blood samples will be donated to the study at the patient's convenience during the exacerbation period. If the patient attends their GP, samples can be retrieved through this route or by sending samples from home.

Bronchoscopy study: Individuals in the study undergoing a clinically indicated bronchoscopy at any time during the follow up period will be asked to donate surplus blood, sputum, biopsies, brushings or bronchial alveolar lavage (BAL) fluid.

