12.0 Data collection and management

12.1 Clinical and demographic data collection

The below are examples of fields already collected by the EMBARC database e.g.- this is not a comprehensive list and other aspects of medical history will be recorded

Age Ethnicity

Gender Height Weight Smoking history Medical history Co-morbidities Number of exacerbations per year Radiological distribution of bronchiectasis on last CT scan Concomitant medications Cause of bronchiectasis and results of diagnostic tests Vaccination history Current physiotherapy techniques Age of diagnosis Previous microbiology and lung function results.

Contact telephone number will be collected for contact to arrange and confirm followup visits and for reminders about exacerbation visits.

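### Exacerbation sampling is voluntary and linked to place of care, and no per-exacerbation record of unsampled events is described, so any Aim 2 cause shares or cluster sizes would describe self-selected attenders and donors

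*Protocol*

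**What the plan says.** The second secondary objective (Protocol 3.2) is broad: "To determine the causes and inflammatory profiles of bronchiectasis exacerbations". It is not limited to exacerbations seen at a study centre.

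The footnote to the visit table (6.0) makes the visit voluntary and gives the reason: "Exacerbation visits are optional as participants treated by their GP or taking a home supply of antibiotics may choose not to attend". A second footnote lets a visit go ahead after 72 hours, with non-response to treatment as its example.

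There are other routes. Section 8.0 invites patients either to attend or to donate through their hospital or GP. Under the exacerbation study in 9.1, where attendance is not possible, "surplus clinical sputum and blood samples will be donated to the study". The same paragraph adds that, for a patient who goes to the GP, samples can be fetched that way or sent from home.

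On records, 12.1 names one exacerbation field, "Number of exacerbations per year", in a list that says it gives examples only. The visit table repeats medical history and concomitant medication at V2-V4, and 21.2 has staff ask about hospitalisations at every visit.

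For Aim 2, 14.2 plans a cluster analysis of the sampled exacerbations, after which "Descriptive statistics will be used to describe the qualities of typical members of each cluster and the differences between clusters".

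On numbers, the visit table gives approximately 300 for the exacerbation visit, while 1.4 says: "Aim 2 will replicate the phenotyping approach to stable patients with 60 patients during exacerbation".

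**The concern.** Whether an exacerbation yields samples depends partly on where it was treated and on the patient's willingness. Place of treatment may well go with severity and presumed cause. If so, the mix of causes and the relative size of clusters among sampled episodes will differ from those among all eligible exacerbations in the cohort.

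Voluntary sampling of unwell people cannot be avoided in a cohort like this. The avoidable part is that the protocol describes nothing that would let a reader see how the sampled episodes differ from the rest: no sampling rule, no log of unsampled episodes with place of treatment, and no comparison of the two. An analysis plan can choose weights, but it cannot weight on a variable that was not collected. That makes this a protocol matter.

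**Working it through.** **Does the selection act among eligible episodes?** The definition in 9.1 requires treatment with antibiotics. Patients treated by the GP or from a supply at home can meet it, so the losses foreseen in 6.0 fall among eligible episodes.

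**Do the other routes close the gap?** Only in part.
- They are voluntary.
- Surplus samples presuppose contact with a clinician, and the send-from-home wording is attached to GP attendance. No route is spelled out for a home-supply patient who sees nobody.
- The surplus route covers sputum and blood. The visit also collects stool and a nasopharyngeal swab, which 9.1 lists for microbiome and viral testing, so evidence on cause may itself differ by route.

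**Do other records fill it?** Medical history and medication entries are not said to hold place of treatment or sampling status. Section 21.2 asks about hospitalisations, but it limits recorded adverse events to those caused by study procedures and excludes worsening of bronchiectasis.

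**Coverage.** There is no derivation to reproduce: 14.1 says the sample sizes were chosen subjectively. From the documents: "In total we will recruit approximately 2500 patients for study", and inclusion applies "if they present with an exacerbation during the 3 year study duration". At most that is 2500 × 3 = 7,500 patient-years. The exacerbation rate and the follow-up achieved are assumptions. Coverage = planned number / (patient-years × rate).

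| Assumed rate per patient-year | Follow-up | Exacerbations | 300 visits | 60 patients, one episode each |
|---|---|---|---|---|
| 0.5 | full | 3,750 | 8.0% | 1.6% |
| 1 | full | 7,500 | 4.0% | 0.8% |
| 2 | full | 15,000 | 2.0% | 0.4% |
| 0.5 | half | 1,875 | 16.0% | 3.2% |

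The 300 comes from the visit column, so donated samples might add to it.

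**Illustrative bias through place of care.** Assume 20% of exacerbations are hospital-treated and k times as likely to be sampled as the others. Hospital share of the sample = 0.2k / (0.2k + 0.8):
- k = 3: 0.6 / 1.4 = 43%
- k = 5: 1.0 / 1.8 = 56%

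True viral share = 0.8 × (home/GP share) + 0.2 × (hospital share). The sampled share uses the sample mix instead.

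| Assumed viral share, home/GP and hospital | True | Sampled, k = 3 | Sampled, k = 5 | Difference in points |
|---|---|---|---|---|
| 50% and 30% | 46% | 41.4% | 38.9% | 4.6 to 7.1 |
| 60% and 20% | 52% | 42.9% | 37.8% | 9.1 to 14.2 |
| equal in both places | any | same | same | 0 |

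For scale, the random 95% half-width at 46% is 1.96 × √(0.46 × 0.54 / n): 5.6 points for n = 300 and 12.6 for n = 60. At 300, a bias of this order would match or exceed sampling error in most of these cases, and more episodes would not shrink it. At 60, random error would mostly dominate.

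**What standardising does.** Reweighting to the recorded mix gives 0.8 × 50% + 0.2 × 30% = 46%, the true value, provided sampling within each place is unrelated to cause. The variance factor is approximately 0.2²/h + 0.8²/(1 − h), where h is the hospital share of the sample: 1.21 for k = 3 and 1.51 for k = 5.

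**What it does not do.** If sampling depends on cause within a place, a true share p with relative sampling chance k appears as pk / (pk + 1 − p). With p = 40% and k = 0.5 to 0.67 that is 25% to 31%, and standardising by place leaves it untouched.

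**The case against.** The strongest reply is that the protocol already softens the problem and promises less than the concern supposes. Four stronger readings are tempting, and the documents support none of them.

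- A reader might infer that only attenders are sampled. It is the visit that is optional; 8.0 and 9.1 give hospital, GP and send-from-home routes, so one of the two groups in the footnote is expressly reached.
- A reader might infer that a yearly count is all that is kept on other exacerbations, so the difference can never be detected. The list in 12.1 is expressly not exhaustive, hospitalisations are asked about, and the registry case report form is not shown. What can be said is that no per-exacerbation record is described.
- A reader might infer that low coverage itself biases the results, or that coverage is known to be a few per cent. Low coverage alone biases nothing, and the protocol gives no exacerbation rate.
- A reader might infer that the cause mix is shown to be wrong. Every bias figure above is assumed, and zero is possible.

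It is also fair that neither 1.4 nor 14.2 promises population cause shares or cluster prevalences. Selection distorts shares more directly than it distorts which clusters exist or how a patient changes from baseline.

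What remains is this: the objective speaks of the causes of exacerbations in general, shares and cluster sizes are a natural thing to report under it, and nothing described would let a reader judge how far they carry over.

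**Conclusion.** The point holds in a limited form and is worth acting on. Exacerbation sampling is voluntary, the protocol itself ties non-attendance to place of care, and the other routes reduce that selection without removing it. Any cause shares or cluster sizes under Aim 2 would describe self-selected attenders and donors.

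The size of any bias is unknown. It is nil if cause is unrelated to place of care and attendance. It is about 5 to 14 points if 20% of exacerbations are hospital-treated, these are three to five times as likely to be sampled, and viral shares differ by place as assumed above. Visit coverage is about 2% to 8% only at 0.5 to 2 exacerbations per patient-year with full follow-up, and up to 16% at 0.5 per year with half the follow-up.

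The 60 patients in 1.4 and the approximately 300 in 6.0 must be reconciled. Coverage and precision depend on which applies, and the statement in 14.1 that all sample sizes exceed 100 fits only the larger.

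**What to change.** 1. At V2-V4, for the remaining follow-up, record one line per exacerbation since the last visit: date, place of treatment (home supply, GP, hospital), and sampled or not. Skip this if the registry case report form already does it, and say so in the protocol. Record place of treatment for every sampled exacerbation.
2. In 14.2, state that the number sampled will be reported over the number recorded, and that Aim 2 results will be described by place of treatment.
3. Where cause shares or cluster sizes are given, put figures standardised to the recorded place-of-treatment mix beside the unweighted ones, and state that selection within a place of care remains.
4. Reconcile the 60 in 1.4 with the approximately 300 in 6.0, and say whether each counts patients or episodes.

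Cost: a few fields at visits already held, with recall over up to 12 months, and about 20% to 50% more variance for the standardised figures under the illustrative assumptions. If 60 is the right number, strata by place will be thin. The study began in August 2018 with a stated duration of 8 years, and this protocol version is dated March 2025, so earlier episodes can be recovered only in part. No extra patients or procedures are needed.
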